We have previously constructed ten standardized case scenarios in an electronic survey format, and ascertained ARV prescribing preferences from experienced HIV clinicians to serve as the reference standard, to define ‘appropriate ART selection’. We will enroll student and resident trainees from Johns Hopkins, who will be randomized to a control group (with access to current DHHS guidelines) or an intervention group (with access to HIV-ASSIST and current guidelines). We will deliver the same ten case scenarios via electronic survey to study participants, who will be asked to recommend ARV regimens for each case. We will report the percent concordance to the reference standard (i.e percent appropriate ART selection), comparing the intervention group to the control group.

2. Objectives

- a) Primary: To determine the difference in percent concordance (with reference standard; i.e. percent appropriate ART selection) between the group using the DHHS guidelines for ARV selection and the group using HIVASSIST for ARV selection.
- b) Secondary: To determine the difference in time for ARV selection for standardized case scenarios between trainees using HIVASSIST and those using the DHHS guidelines.

3. Background

The Centers for Disease Control and Prevention (CDC) estimate that 1.2 million people currently live with HIV in the United States; however, only less than half have been prescribed antiretroviral (ARV) therapy and are virally suppressed. ARV regimens generally include multiple drugs from various mechanistic classes. There are currently over 30 ARV drugs in 7 different classes that have been approved by the U.S. Food and Drug Administration (FDA), leading to a wide array of potential ARV combinations.

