- b. Study participants and settings: We will enroll up to 200 participants. Students in the Johns Hopkins University SOM or SON (Baltimore, Maryland), and/or internal medicine residents at Johns Hopkins Hospital will be eligible to participate. Participants will be invited to participate via an email to class or program listservs or via flyers posted in the school of medicine or nursing buildings. Individuals that are interested will have a link to a Qualtrics survey where they will receive additional study details.
- c. Enrollment/Randomization: An email will describe the study and will contain a link to the survey; the email will also inform them that their participation is completely voluntary, and that their decision to participate (or not) will in no way affect their academic standing. They will also be informed that no information about individual results/surveys will be shared with their school administration. All participants enrolling in the study will be offered an incentive of \$50 gift card or equivalent; they will receive a link to this gift card via email after their participation. Study enrollment will take place over 12 months. Participants will be recruited on a rolling basis throughout the study period.
 - Qualtrics will be used to deliver the survey, including an initial page explaining the study and asking for consent.
 - Qualtrics will automatically randomize participants to different groups as a part of the survey process, using Qualtrics internal random sequence generator. We do not include any stratifications for randomization as limited demographic detail is collected. The participants were not blinded to their allocation, as they were told which decision-support aids they would have available.
 - The survey will be conducted in one session, and the time to complete the survey will be captured. Individuals not completing the survey in one session will be excluded.
- d. Data collection/Survey:

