 - Development of standardized case scenarios: We have previously designed 10 clinical case scenarios for a range of patient situations, including a) ARV naïve b) ARV experienced, suppressed or c) ARV experienced, failing patients (with and without mutations, comorbidities, and common co-medications). In a prior prospective survey, we have ascertained ARV preferences for each case scenario among a cohort of experienced HIV clinicians. These ARV choices for each case scenario will be considered a reference standard to judge acceptability of ARV selections in the study cohort in this study.
 - We will collect basic demographic details of study participant including degree program (NP,MD), level of training (M1, M2), and level of experience with HIV care.
 - Each survey will have its own video tutorial briefly explaining how to use the DHHS guidelines and/or HIV-ASSIST. A link to the video will be provided in the survey. The control group will have a link to the DHHS guidelines in the survey. The experimental group will have a link to both the DHHS guidelines, and the HIVASSIST tool. Each participant must acknowledge that they have successfully accessed their respective resources to help inform their ARV regimen selections. A question at the beginning of both surveys will restrict the participants from

advancing until they have filled information from either DHHS guidelines or HIV-ASSIST correctly. This will be a test of the participant's understanding of how to use the survey and the respective regimen selection aid.

- Study participants will be guided through a survey in which the ten standardized case scenarios (vignettes with relevant HIV and patient variables are provided) are presented, and participants will be asked to propose their ARV treatment regimens. The participant's ARV choices will be recorded. Through Qualtrics software, we will also record the time needed to complete the study.

e. Statistical considerations:

Definitions of appropriate ART selection:

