Current DHHS guidelines recommend an individualized approach to ARV selection based on multiple considerations. Several regimens are listed as acceptable for ARV-naïve patients as 'regimens recommended for most people living with HIV', with specific instructions on comorbidities or drug interactions that may lead to selection from a list of 'regimens recommended in some clinical scenarios'. For ARV-experienced patients, the guidelines outline a list of general treatment principles to consider, such as including "at least two, and preferably three, fully active agents."

For each case-scenario in the survey, we have previously collected ARV selections from a cohort of experienced HIV clinicians, recognizing that there may be multiple reasonable ARV regimen options for each case scenario. The ARV choices from the prior survey will be used as the reference standard.

Each question will be graded as 'concordant/appropriate' if the ARV regimens selected by the respondent matches an ARV regimen of any HIV expert, or is consistent with current DHHS guidelines (e.g., selection from the list of "regimens recommended for most people living with HIV" for treatment-naïve case-scenarios; regimens which "include at least two, and preferably three, fully active agents")

Our primary outcome is the proportion of appropriate ARV selection for standardized case scenarios, comparing between trainees and expert HIV clinicians and/or DHHS guidelines. Specifically, we will assess:

- a) The difference in percent appropriate/concordant between the control group, and the intervention group that has access to HIV-ASSIST

Hypothesis: There will be a statistically significant higher percent concordance in the group using HIV-ASSIST compared to the group using DHHS guidelines alone.

Our secondary outcome will look at the time required for each group to reach a correct answer. Specifically, we will assess:

b) The difference in time to ARV selection for standardized case scenarios between trainees using HIV-ASSIST and those using the DHHS guidelines.

Hypothesis: There will be a statistically significant lower time to correct ARV selection in the group using HIV-ASSIST compared to the group using DHHS guidelines.

Sample Size:

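### The secondary time outcome has two definitions, and the one in the hypothesis (time to a correct selection) conditions on the primary outcome and needs per-case timing that the plan does not describe

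*Combined protocol and SAP*

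**What the plan says.** Four statements define the time outcome.

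- Section 2, Objectives, b): "To determine the difference in time for ARV selection for standardized case scenarios between trainees using HIVASSIST and those using the DHHS guidelines". There is no condition on correctness.
- Section 3 (Study Procedures), item e, lead sentence on the secondary outcome: "Our secondary outcome will look at the time required for each group to reach a correct answer". Conditional on correctness.
- Item e, b): "The difference in time to ARV selection for standardized case scenarios between trainees using HIV-ASSIST and those using the DHHS guidelines". No condition.
- Item e, hypothesis under b): "There will be a statistically significant lower time to correct ARV selection in the group using HIV-ASSIST". Conditional.

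Timing is described twice. Item c says "the time to complete the survey will be captured", and item d says "we will also record the time needed to complete the study". No timer per case or per page is mentioned.

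An opening question stops participants from "advancing until they have filled information from either DHHS guidelines or HIV-ASSIST correctly". For the ten cases, "participants will be asked to propose their ARV treatment regimens", and no feedback or second attempt is described. The plan gives no rule for the time of a wrongly answered case, and no analysis method for time.

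**The concern.** Two of the four statements ask how long participants take to choose a regimen. The other two ask how long they take to choose an appropriate one. These are different quantities, and the same data can give different answers to them.

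The conditional version has two problems of its own.

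1. If only a whole-survey time exists, it cannot be divided between correct and incorrect cases, so a per-case time to correct selection cannot be computed.
2. If per-case times exist, keeping only the correct ones selects on the primary outcome, which the tool is expected to change. The arms may then be timed on different cases and different participants, and randomisation no longer protects the comparison.

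At stake is the claim that the tool makes trainees faster. Selection alone could produce, hide or reverse a speed difference. With two definitions and no stated analysis, the choice could also be made after the data are seen.

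**Working it through.** The documents give no effect, SD or sample size for time, so there is no stated figure to reproduce.

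**Inputs from the documents.** Ten cases per participant; control mean 0.5 with SD up to 0.5 (0.3 is also used in Table 1); intervention mean 0.8 with SD 0.1; 18 per arm.

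**Step 1: cases kept.** Control 10 × 0.5 = 5; intervention 10 × 0.8 = 8. Correct-only time drops 50% of control case times and 20% of intervention case times.

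**Step 2: participants with no time value.** A score between 0 and 1 with mean 0.5 has a maximum SD of √(0.5 × 0.5) = 0.5, reached only if every score is 0 or 1. At the plan's upper-bound SD, half the control arm (9 of 18) would have no correct answer.

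For SD 0.3, take a beta-binomial score: 0.25 × (1 + 9ρ)/10 = 0.09 gives ρ = 0.289 and both beta parameters equal to ½(1/ρ − 1) = 1.23. The chance of no correct answer is the product over i = 0 to 9 of (1.23 + i)/(2.46 + i), which is 0.072, or about 1 of 18. A logistic-normal model gives 0.070 to 0.073. In the intervention arm, a binomial at 0.8 gives 0.2^10, about 1 in 10 million.

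**Step 3: illustration with no true time effect.** Everything in this step apart from the inputs above is assumed.

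- Ten difficulty levels d run evenly from −1.5 to 1.5.
- The probability of a correct answer is logistic in d with slope −1.0 or −1.5; intercepts give means of 0.5 and 0.8.
- Case time is 3·exp(s·d) minutes in both arms.
- The intervention arm has no spread in ability (score SD 0.11 to 0.12).
- The control arm has no ability spread (SD 0.13 to 0.14), a normal ability effect giving SD 0.3, or all-or-none scores (SD 0.5).

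Mean time among correct answers in an arm is Σp(d)·time(d)/Σp(d). For slope 1.0, s = 0.3 and no ability spread, this is 2.973 min for intervention and 2.751 min for control, a ratio of 1.081. With all-or-none control scores, control keeps easy and hard cases equally (3.125 min), and the ratio is 2.973/3.125 = 0.951.

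Ratios, intervention/control (slope 1.0, slope 1.5):

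| s | control SD 0.13–0.14 | SD 0.3 | SD 0.5 |
|---|---|---|---|
| −0.3 | 0.934, 0.914 | 0.965, 0.956 | 1.046, 1.059 |
| 0 | 1.000, 1.000 | 1.000, 1.000 | 1.000, 1.000 |
| 0.3 | 1.081, 1.112 | 1.038, 1.049 | 0.951, 0.935 |
| 0.5 | 1.141, 1.201 | 1.063, 1.082 | 0.920, 0.892 |

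The true ratio is 1 in every cell. The ratio is also 1 if accuracy is unrelated to difficulty.

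**Step 4: false-positive rates.** 2000 simulated trials per setting, 18 per arm, s = 0.3, log-time SDs 0.3 between and 0.4 within participants (assumed), Welch test on one value per participant at a nominal 5%.

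- Correct answers, unadjusted: 12–18%, 10–13% and 7–8% for the three control SDs in turn.
- Correct answers centred by case: 4–6% over all settings run.
- All ten cases: 4–6%.

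**Step 5: participant selection.** Centring by case does not correct for which participants remain. Assume a correlation of ±0.5 between control ability and the participant's log-time level. With all-or-none scores, those kept are the upper half in ability, whose mean ability is 0.798 SD, so the closed form for the case-adjusted ratio is exp(±0.3 × 0.5 × 0.798) = 1.127 or 0.887. Simulation gives 1.126–1.128 or 0.891, with about 14% false positives. At SD 0.3 the ratio is 0.98 to 1.02 with 5–6% false positives. Using all ten cases, the rate stays at about 5%.

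**The case against.** The best defence is that item b) is the operative definition. It follows a phrase introducing the specific assessment, it matches the Section 2 objective almost word for word, and it fits the whole-survey timing. 'Correct' would then be loose wording. That reading is fair, but the condition is also in the hypothesis to be tested, so the text still needs correcting.

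The plan's silence does not show that page timers or retries are absent. That stands, and the computability point is conditional for that reason.

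A third reading is total time per correct answer, which whole-survey time would support. It also mixes in the primary effect: with equal total times and 5 versus 8 correct, the ratio is 5/8 = 0.625, an apparent 37.5% saving with no difference in speed. It is undefined for a score of zero.

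The numbers have real limits. The SD of 0.5 is a planning cap, so 9 of 18 is an extreme and the 7% at SD 0.3 is more informative. The false-positive rates depend on the summary tested: mean log time gives 11–14%, 9–10% and 6–8%. They also depend on sample size. The plan allows up to 200 participants, and at 100 per arm mean log time gives 36–56%, 24–40% and 14–21%. These rates illustrate the mechanism and are not properties of the plan.

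Two limits of the remedy also stand. Unconditional time credits fast wrong answers, so it should be read beside the accuracy result. The exclusion of participants who do not finish in one session may be related to time, and it affects any definition.

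**Conclusion.** The concern holds. The two definitions stand side by side in the current text, and the hypothesis uses the one that randomisation does not protect. On the plan's own rates, about 5 versus 8 of 10 cases per participant would be compared. At a control SD of 0.3, about 7% of control participants would have no time value, rising to half at the SD cap.

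The bias itself cannot be sized or signed from the documents. Under the assumptions in the working, a true ratio of 1 appears as 0.91 to 1.11 for s = ±0.3, in either direction, and it stays at 1.00 if difficulty is unrelated to time or to accuracy.

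Confidence is high in the inconsistency and in the selection after randomisation, but not in any particular bias figure. The outcome is secondary and the primary is untouched, so this should be corrected but does not threaten the main result.

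**What to change.** - In Section 3 (Study Procedures), item e, reword the lead sentence and the hypothesis to the unconditional definition already used in item b) and the Section 2 objective.
- State what is timed. Use page times for each case if the survey records or can record them.
- Compare time over all ten cases regardless of correctness, by randomised arm, with the participant as the unit (for example, log total case time).
- If only total survey time is available, compare that and state that it may include the consent page, the arm-specific tutorial and the opening question.
- Report time among correct answers as a supportive analysis adjusted for case, with the number per arm who have no correct answer. Do not use it as the hypothesis test.
- Report exclusions for not finishing in one session by arm, since they bear on any time comparison.

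The cost is two reworded sentences, a statement of what is timed and, if absent, page timers. If the survey can no longer be changed, only the total-time comparison is available and set-up time stays in the measure. The plan gives up time to a correct answer as its headline claim.

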There is limited a priori data to estimate the likely percent concordance between trainees/students and HIV experts. We assumed that those participants using DHHS guidelines alone (control) will have an average of up to 50% appropriate responses, with a wide standard deviation of up to 0.5. We anticipate that there will be approximately 80% appropriate ART selections with a standard deviation of 0.1 among those in the intervention arm. With this assumption, we would need 18 individuals in each arm to be adequately powered to detect a difference (two-sided alpha, 0.05). Table 1 shows needed sample size to have 80% power to detect a difference between the control and intervention arms under varying assumptions. In secondary analysis, we will compare the control and intervention arms, stratified by level of training.

DHHS MEAN % APPROPRIATE RESPONSES	0.3	0.3	0.3	0.5	0.5	0.5	0.3	0.3	0.3	0.5	0.5	0.5
HIVASSIST MEAN % APPROPRIATE RESPONSES	0.7	0.7	0.7	0.7	0.7	0.7	0.8	0.8	0.8	0.8	0.8	0.8
DHHS SD	0.1	0.3	0.5	0.1	0.3	0.5	0.1	0.3	0.5	0.1	0.3	0.5
HIVASSIST SD	0.1	0.1	0.1	0.1	0.1	0.1	0.1	0.1	0.1	0.1	0.1	0.1
Sample size needed per group for 80% power	1	4	11	4	16	41	1	1	7	2	7	18

Table 1. Sample Size Variations by Expected Group Means and Standard Deviations

4. Drugs/ Substances/ Devices

a. N/A

5. Risks

a. This study only involves a survey with standardized cases to ascertain clinician preferences for a variety of HIV case scenarios. Participants may feel insecure regarding their self-perceived lack of knowledge regarding HIV management. However, all responses to the survey will be visible only to the study members. There are no other biological risks identified.

- b. Steps taken to minimize the risks.: Participants will be permitted to stop participating in the survey at any time.
- c. Plan for reporting unanticipated problems or study deviations: Participants will be instructed to contact the PI if any problems occur during survey completions. Such problems will be reported to the IRB immediately.
- d. Financial risks to the participants: There are no financial risks to participants.

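### The stated 18 per arm gives about 66–70% power at two-sided 0.05, not 80%; the plan's own inputs need 23 to 25, and seven other Table 1 entries are also too small

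*Combined protocol and SAP*

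**What the plan says.** All the relevant text is in the combined protocol and SAP, Study Procedures, item e, under Sample Size, apart from the enrolment limit in item b.

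- **Control arm:** participants using the DHHS guidelines alone "will have an average of up to 50% appropriate responses", "with a wide standard deviation of up to 0.5".
- **Intervention arm:** "approximately 80% appropriate ART selections with a standard deviation of 0.1 among those in the intervention arm".
- **Conclusion:** "With this assumption, we would need 18 individuals in each arm to be adequately powered to detect a difference (two-sided alpha, 0.05").
- **Power:** the next sentence says "Table 1 shows needed sample size to have 80% power to detect a difference between the control and intervention arms under varying assumptions", and the results row of Table 1 is labelled "Sample size needed per group for 80% power". The last column has the same means and SDs as the text and the same answer, 18.
- **Enrolment (item b):** "We will enroll up to 200 participants". No minimum is given.

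The plan names no statistical test or formula for the calculation. Participants who do not finish in one session are excluded (item c), and the sample size makes no allowance for this.

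**The concern.** The means, SDs, alpha, sidedness and power are all stated, so the sample size follows from them and can be checked. The printed 18 is about a fifth below the result, and most other entries in the row fall short as well, which points to a different alpha or power from the one stated. This paragraph and table are the plan's only power justification. A team that took 18 completers per arm as sufficient would run the primary comparison with roughly a one-in-three chance of missing the assumed 30-point difference, rather than one in five.

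**Working it through.** **Inputs** (Sample Size paragraph and Table 1, last column): means 0.5 and 0.8, so the difference is 0.3; SDs 0.5 and 0.1, so the variances sum to 0.25 + 0.01 = 0.26; equal arms; two-sided alpha 0.05; power 80%.

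**Formula** (two means, unequal SDs, normal approximation, rounded up):
n per arm = (z_alpha + z_power)² × (SD0² + SD1²) / difference²

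**Step 1: what reproduces the printed 18**

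- One-sided 0.05, 80% power: (1.645 + 0.842)² = 6.183; 6.183 × 0.26 / 0.09 = 17.86, so 18.
- Two-sided 0.05, 70% power: (1.960 + 0.524)² = 6.172; 6.172 × 0.26 / 0.09 = 17.83, so 18.

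Other variants do not give 18. A one-sided t-test gives 19 (pooled) or 20 (Welch). A comparison of two proportions gives 39 two-sided or 31 one-sided.

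**Step 2: the calculation as stated**

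Two-sided 0.05, 80% power: (1.960 + 0.842)² = 7.849; 7.849 × 0.26 / 0.09 = 22.67, so **23**.

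| Method (two-sided 0.05) | n per arm for 80% | Power at that n | Power at 18 |
|---|---|---|---|
| Normal | 23 | 80.6% | 70.4% |
| Pooled t | 24 | 80.6% | 67.9% |
| Welch t | 25 | 80.8% | 65.7% |

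Simulation with normally distributed scores agrees at 18 per arm (about 68% pooled, 66% Welch). By the normal formula, the difference detectable with 80% power at 18 per arm is √(7.849 × 0.26 / 18) = 0.34; it is up to 0.36 with a t-test.

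**Step 3: the whole of Table 1** (columns numbered from the left; intervention SD 0.1 throughout; the last column is two-sided normal power)

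| Col | Means | Control SD | Printed | Two-sided 80%, normal | Two-sided 80%, pooled t | One-sided 80%, normal | Power at printed n |
|---|---|---|---|---|---|---|---|
| 1 | 0.3, 0.7 | 0.1 | 1 | 1 | 3 | 1 | 80.7% |
| 2 | 0.3, 0.7 | 0.3 | 4 | **5** | 7 | 4 | 71.6% |
| 3 | 0.3, 0.7 | 0.5 | 11 | **13** | 14 | 11 | 74.0% |
| 4 | 0.5, 0.7 | 0.1 | 4 | 4 | 6 | 4 | 80.7% |
| 5 | 0.5, 0.7 | 0.3 | 16 | **20** | 21 | 16 | 71.6% |
| 6 | 0.5, 0.7 | 0.5 | 41 | **52** | 52 | 41 | 70.9% |
| 7 | 0.3, 0.8 | 0.1 | 1 | 1 | 3 | 1 | 94.2% |
| 8 | 0.3, 0.8 | 0.3 | 1 | **4** | 5 | 3 | about 35% |
| 9 | 0.3, 0.8 | 0.5 | 7 | **9** | 10 | 7 | 73.7% |
| 10 | 0.5, 0.8 | 0.1 | 2 | 2 | 4 | 2 | 85.1% |
| 11 | 0.5, 0.8 | 0.3 | 7 | **9** | 10 | 7 | 70.9% |
| 12 | 0.5, 0.8 | 0.5 | 18 | **23** | 24 | 18 | 70.4% |

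Eight entries (bold) are too small by the normal formula: the headline column and seven others. With a t-test all 12 are too small. The one-sided row matches the printed row in 11 of 12 columns. Two-sided 0.05 at 70% power gives the same row after rounding, so the table cannot show which was used. Column 8 matches neither.

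**Step 4: attainable SDs**

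For a score between 0 and 1 with mean m, the SD cannot exceed √(m(1 − m)). At m = 0.5 this is 0.5, so the headline uses the limiting case. At m = 0.3 it is √0.21 = 0.458, so the SD of 0.5 in columns 3 and 9 is not possible. At 0.458 the two-sided normal n is 7.849 × 0.22 / 0.16 = 10.8, so 11 (column 3), and 7.849 × 0.22 / 0.25 = 6.9, so 7 (column 9).

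**The case against.** The strongest counter-argument is about consequence.

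- **Enrolment.** The plan allows up to 200 participants. Under the headline assumptions power is about 98% at 50 per arm and above 99.9% at 100 per arm. This stands, but 200 is a ceiling with no stated floor, and 18 is the only requirement the plan gives.
- **Conservative inputs.** The control SD is given as an upper value, and 0.5 would require every control participant to score 0% or 100%. Eighteen per arm would suffice if that SD were at most about 0.44 (normal), 0.43 (pooled t) or 0.42 (Welch). At SD 0.4 it gives 83–87% power. This also stands, but the plan claims that 18 suffices at 0.5.
- **Wording.** The sentence containing 18 gives no power percentage. The next sentence and the table row do, for identical inputs and the same n.
- **Direction.** The hypothesis is that HIV-ASSIST does better, so a one-sided test might have been intended. The sample-size text says two-sided; if that is the slip, the text still needs correcting.
- **The count of eight.** It depends on the normal formula, which is unreliable at very small n, and several shortfalls are only one or two participants. Columns 3 and 9 are short only for their labelled, unattainable SD; at 0.458 the printed 11 and 7 are enough by that formula. Column 8 rests on one digit in a table extracted from PDF and may be a typing or extraction slip.

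These points limit the weight of the finding. None makes 18 correct for the stated inputs.

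**Conclusion.** The concern holds. With means 0.5 and 0.8, SDs 0.5 and 0.1, two-sided alpha 0.05 and 80% power, the requirement is 23 per arm (normal), 24 (pooled t) or 25 (Welch), before any allowance for excluded non-completers. Eighteen gives about 66–70% power. Seven further entries in Table 1 are too small for their labelled inputs by the normal formula. The pattern fits either a one-sided calculation labelled two-sided or a power of 70% labelled 80%, and the document cannot settle which. Column 8 is a separate discrepancy.

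This should be fixed as an error in the stated figures. It is not a reason to raise enrolment: a trial that recruits well beyond 18 per arm is adequately powered under these assumptions.

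**What to change.** 1. Restate the headline as 23 per arm at two-sided 0.05 and 80% power (24 pooled t, 25 Welch), or keep 18 and state its power as about 66–70%. If the calculation was in fact one-sided, say so and reconcile it with the stated two-sided alpha.
2. Name the test and recompute Table 1 for it at two-sided 0.05. The pooled-t row for columns 1–12 is 3, 7, 14, 6, 21, 52, 3, 5, 10, 4, 10, 24. The normal row is 1, 5, 13, 4, 20, 52, 1, 4, 9, 2, 9, 23. The t-based row is preferable, since one participant per group gives no estimate of within-group variance.
3. Check column 8 against the source calculation.
4. As a minor correction, replace SD 0.5 at mean 0.3 (columns 3 and 9) with a value no greater than 0.458, and recompute those two entries.
5. Ideally, state the planned minimum number of completers per arm next to the cap of 200.

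The cost is one or two sentences and corrections within one table. If the two-sided 0.05 is kept, the endpoint, alpha and enrolment cap are unchanged.
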